#### **10.6 Follow-up Assessment**

Subjects will exit the study at the end of postoperative day 30 (midnight). Clinical data will be collected through 30 days post index surgery. This will include readmission for diagnosed POAF and/or RBS related occurrences within 30 days after the index surgery. The patient will be considered as exited from the study at end of day 30 (midnight) post index surgery for the purposes of clinical data collection.

#### **10.7 Study Termination**

Subject participation is terminated at day 31 post index surgery.

If a subject is re-admitted within 30 days after the index surgery to the treating hospital, a satellite clinic, or another hospital for any diagnosis of RBS and/or POAF-related occurrences, clinical data will be collected.

Table 2: Subject	participation and dat	a collection period
------------------	-----------------------	---------------------

	Discharge <30d*	Discharge >30d
Clinical	Y	Ν
data		

\* Including re-admission for RBS and/or POAF-related occurrences <30d.

# **11** Safety Assessment and Medical Device Reporting

The PleuraFlow® System is a Class II device in the US and approved device in Canada and a Class IIa device per rule 7 of Annex IX of Directive 93/42/EEC. In its issuance of a substantial equivalence determination, the FDA did not require Sponsor to conduct a PMCF study. This PMFC study is conducted on label. Being marketed also in the European Community (EC), this study has to meet post-market surveillance requirements. In the preface of MEDDEV 2.12/2 Rev 2 "Post Market Clinical Follow-Up Studies, A Guide for Manufacturers and Notified Bodies" it is stated: "Similarly when PMCF studies are conducted using CE Marked devices within their intended use, the provisions of Section 2.3.5 of Annex X of Directive 93/42/EEC do not apply. However, the provisions of Directive 93/42/EEC concerning information and notification of incidents occurring following placing devices on the market are fully applicable.

Sponsor is subject to all requirements of 21 CFR Part 803 (MDR Reporting). Accordingly, Sponsor shall report all MDR reportable events (see definition) to FDA on Form FDA 3500A. Sponsor shall review and evaluate all complaints (see definition) to determine whether a complaint represents an event that must be reported to FDA. Sponsor shall report an event upon becoming aware of information that reasonably suggests that the PleuraFlow® System has or may have caused or contributed to a death, serious injury, or has malfunctioned and that the device would be likely to cause or contribute to a death or serious injury if the malfunction were to recur. Serious injuries where the device would be likely the cause of or contributed to shall be followed to resolution.

The PI will evaluate and determine if the PleuraFlow® System has or may have caused or contributed to a death, serious injury, or has malfunctioned. Sponsor has the right to request the steering committee to review the PI decision and concur or disagree. In case the steering committee and PI disagree the steering committee adjudication prevails.

#### **11.1 Definitions**

Serious injury /(Serious illness) [21 CFR part 803.3(aa)(1)] is an injury or illness that:

- is life threatening, even if temporary in nature;
- results in permanent impairment of a body function or permanent damage to a body structure; or
- necessitates medical or surgical intervention to preclude permanent impairment of a body function or permanent damage to a body structure.
- A malfunction [21 CFR Part 803.3(m)] is a failure of the device to meet its performance specifications or otherwise perform as intended. Performance specifications include all claims made in the labeling for the device. A malfunction should be considered reportable if any one of the following is true:
- the chance of a death or serious injury occurring as a result of a recurrence of the malfunction is not remote;
- the consequences of the malfunction affect the device in a catastrophic manner that may lead to a death or serious injury;
- it causes the device to fail to perform its essential function and compromises the device's therapeutic, monitoring or diagnostic effectiveness, which could cause or contribute to a death or serious injury, or other significant adverse device experiences. The essential function of a device refers not only to the device's labeled use, but for any use widely prescribed within the practice of medicine;

- it involves an implant malfunction that would be likely to cause or contribute to death or serious injury, regardless of how the device is used;
- the device is considered life-supporting or life-sustaining, and thus essential to maintaining human life; or

#### **11.2 Reporting Requirements**

Investigators shall report to Sponsor PleuraFlow-related serious injuries as soon as becoming aware of the injury and no later than 48 hours.

Investigators shall report deaths to both the Sponsor and Regulatory authorities in compliance with their applicable State, Country and conditions imposed by the reviewing Institutional Review Board (IRB).

Sponsor shall take action under 21 CFR part 518 or part 806 of the FD&C Act as a result of the malfunction of the device.

Sponsor shall also take action under MEDDEV 2.12/1 rev 8 Guidelines on a Medical Devices Vigilance System and under Health Canada Medical Device Regulations SOR/98-282, since the device is marketed under a CE Marking and Health Canada license.

Sponsor's reporting requirements are listed in Table 3.

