#### Rev. 4, Febuary 2016

- 2.13.2 Secondary performance endpoints
  - Rate of interventions to treat Retained Blood Syndrome (RBS). RBS is a composite endpoint defined as an intervention to treat one or more of the following conditions:

-Re-exploration for bleeding, tamponade or washout of retained blood [Time Frame: discharge from OR to 30 days post index surgery];

-Any procedure to treat Pericardial effusion; i.e., pericardial window, pericardiocentesis, placement of pericardial drain [Time Frame: discharge from OR to 30 days post index surgery];

-Any procedure to treat Pleural effusion; i.e., thoracentesis under any image-guided modality [Time Frame: discharge from OR to 30 days post index surgery];

-Any procedure to treat hemothorax (i.e., chest tube, thoracoscopy, thoracotomy, etc.) [Time Frame: discharge from OR to 30 days post index surgery]Any procedure to treat Pneumothorax. [Time Frame: discharge from OR to 30 days post index surgery].

- Readmission for any diagnosis of RBS and/or POAFrelated occurrences [Time Frame: within 30 days post index surgery].
- Readmission for any reason. [Time Frame: within 30 days post index surgery].

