#### 2.13.3 Other Outcomes:

- Mortality [Time Frame: within 30 days post index surgery];
- Length of Hospital Stay [Time Frame: day of discharge];
- Stay in the Intensive Care Unit (ICU) [Time Frame: hours];
- Ventilation time [Time Frame: hours to extubation];
- Transfusion postoperative [Time Frame: total number and type of units used];
- Total chest tube output first 24 hours [Units: milliliters];
- Total chest tube drainage [Units: milliliters];

•	Any cardiac arrest [Time Frame: within 30 days post index surgery];
•	Stroke [Time Frame: within 30 days post index surgery];
•	Renal failure requiring dialysis [Time Frame: within 30 days post index surgery];
-	Renal insufficiency with serum creatinine level 3 times greater than baseline level or serum creat level $\geq$ 300 $\mu$ mol/L. [Time Frame: within 30 days post index surgery]; converter en umol/L pour nous.
•	Surgical Site Infection:
dui	-Sternal Superficial Wound Infection: (i) within 30 days st index surgery; (ii) 30 days post index surgery but ring hospitalization; (will be confirmed at postoperative rgeon appointment)
	-Deep Sternal Infection/Mediastinitis; within 30 days st index surgery (will be confirmed at postoperative geon appointment)
(wi	-Post-op Pneumonia; within 30 days post index surgery ill be confirmed at postoperative surgeon appointment)
	Septicemia [Time Frame: hospital discharge];
•	Sepsis [Time Frame: within 30 days post index surgery];
•	Urinary tract infection [Time Frame: within 30 days post index surgery];
Data	Management:
of Mo	will be collected and stored at the department of surgery ntreal Heart Institute. Only the princiapal investigator tudy coordinators will have access to the database.
Stat	istics
Samp	ole Size Calculations:
analy: the P	primary analysis will be an intention-to-treat (ITT) sis comparing the POAF rate in the PleuraFlow ® group to OAF rate in the control group. Based on findings from our utional clinical database at the Montreal Heart Institute,

the local incidence of POAF after cardiac surgery is approximately 25% (control group). The proportion in group Pleuraflow (the treatment group) is assumed to be 0,2500 under the null hypothesis and 0,1500 under the alternative hypothesis. Group sample sizes of 254 in each group achieve 80% power to detect a difference between the group

Rev. 4, Febuary 2016

2.14

2.15

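### Serious injuries outside the listed endpoints are reported only if attributed to PleuraFlow, and tube malfunction or replacement is not an outcome, so these events cannot be compared between arms

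*Combined protocol and SAP*

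**What the plan says.** Section 11.2 sets the investigator's duty on injuries: "Investigators shall report to Sponsor PleuraFlow-related serious injuries as soon as becoming aware of the injury and no later than 48 hours". Section 11 gives the causality judgement the same product scope: "The PI will evaluate and determine if the PleuraFlow ® System has or may have caused or contributed to a death, serious injury, or has malfunctioned". Follow-up is limited in the same way: "Serious injuries where the device would be likely the cause of or contributed to shall be followed to resolution".

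Deaths are treated differently. Section 11.2 says "Investigators shall report deaths to both the Sponsor and Regulatory authorities", with no limit by product or arm.

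The endpoints in 2.13.2 and 2.13.3 apply to all randomised patients. They include "Re-exploration for bleeding, tamponade or washout of retained blood [Time Frame: discharge from OR to 30 days post index surgery", "Any procedure to treat hemothorax", "Any procedure to treat Pneumothorax. [Time Frame: discharge from OR to 30 days post index surgery" and "Mortality [Time Frame: within 30 days post index surgery". The synopsis section on statistical analysis compares all categorical event rates between arms by chi-square test.

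In section 14.4 the sponsor undertakes to look into every adverse event. No section gives investigators a matching rule to collect adverse events in both arms.

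**The concern.** The randomised difference in this trial is the chest tube. Section 5 describes a metal wire that moves inside the test tube, and section 4 builds the rationale on tube obstruction. The second objective in 2.4 extends to other complications after cardiac surgery, so comparing tube-related harm and tube failure is within the trial's scope.

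The only questions in the protocol about tube injury or tube malfunction are vigilance questions about one product. It is proper for vigilance to be limited to the sponsor's product, but a randomised comparison needs the same question asked in both arms. What is not asked of control patients during the trial may not be recoverable at analysis. At stake is what the trial can say about injuries and tube failures that do not lead to one of the listed procedures or outcomes.

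**Working it through.** The point rests on reading sections against each other. The arithmetic only illustrates size.

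**1. Scope of each safety duty**

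| Duty | Section | Applies to |
|---|---|---|
| Serious-injury report within 48 hours | 11.2 | PleuraFlow-related injuries |
| Judgement of causality and malfunction | 11 | PleuraFlow System |
| Follow-up of injury to resolution | 11 | Injuries attributed to the device |
| Manufacturer reporting timelines | Table 3 | The manufacturer's product |
| Death report | 11.2 | All deaths |
| Sponsor's investigation of adverse events | 14.4 | All, but with no investigator collection rule |

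SAE and UADE appear in the abbreviation list without a collection rule in the text. Item 13.9 sends investigators to section 12.2 for reporting requirements, but 12.2 is Data Monitoring.

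**2. What is collected in both arms**

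- Section 2.13.2: re-exploration, procedures for pericardial effusion, pleural effusion, hemothorax and pneumothorax, and readmission.
- Section 2.13.3: mortality, cardiac arrest, stroke, renal outcomes, sternal infection and mediastinitis, pneumonia, sepsis, transfusion, chest tube output and others.
- Not listed: tube injury, malfunction, blockage, dislodgement or replacement. Drainage volume does not show whether a tube failed. Section 12.1 mentions patency only through optional photographs.

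**3. Four events traced through these rules**

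- *Tube injury that bleeds and leads to re-exploration.* Counted in both arms, within the retained blood composite.
- *Injury meeting the 11.1 definition, managed without any listed procedure or outcome.* Reported if attributed to PleuraFlow. No stated route if attributed to a standard tube, either in a control patient or in a test patient, who may also have up to two standard tubes (8.1).
- *Tube replaced for blockage or dislodgement.* Not an outcome in either arm. A PleuraFlow failure may reach the investigator's malfunction assessment; a standard-tube failure has no equivalent.
- *Death.* Reported and compared in both arms.

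The gap is the second and third events.

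**4. Illustration of size**

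First the plan's sample size. With p1 = 0.25, p2 = 0.15, two-sided alpha 0.0476 (z = 1.981), power 80% (z = 0.842) and mean proportion 0.20:

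n = [1.981 × √(2 × 0.20 × 0.80) + 0.842 × √(0.25 × 0.75 + 0.15 × 0.85)]² / 0.10² = (1.121 + 0.472)² / 0.01 ≈ 254 per arm.

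The stated 254 reproduces.

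The event counts below are assumptions, because the documents give no tube-injury rate. For 6 injuries among 254 test patients (6/254 = 2.4%), two-sided Fisher exact tests give:

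| Control count | p |
|---|---|
| 0/254 | 0.03 |
| 3/254 | 0.50 |
| 6/254 | 1.0 |

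Without the control count, the data cannot distinguish these cases. If the test arm had no events, the one-sided 95% upper limit would be 1 − 0.05^(1/254) = 1.2%, again without a comparator.

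Precision stays limited even with both arms collected. At 254 per arm, two-sided 0.05 and 80% power, a normal approximation (rough at such low rates) gives detectable contrasts of about 0.5% vs 4.3%, 1% vs 5.3%, 2% vs 7.2% and 5% vs 11.9%.

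**The case against.** The strongest case against is that the harms that matter most are already compared. A serious injury to lung or heart would often lead to a pneumothorax or hemothorax procedure, tamponade with re-exploration, a pericardial procedure, cardiac arrest or death, and each is recorded in both arms. A randomised comparison of event rates does not need attribution to the tube. This stands, and it limits the point to events outside those lists.

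A reader might infer from 11.2 that chest-tube harm is collected in the test arm alone, or that the trial cannot compare it at all. The endpoint lists and the chi-square comparison contradict both. A reader might also infer a bias against the device from one-sided counts. The documents do not support that either: section 11 is vigilance reporting, and no section makes 11.2 reports a trial outcome or tabulates them by arm.

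Section 12 places the CRF samples in a Manual of Operation that is not among the documents, and 14.8 has the sponsor keep adverse-event records. Wider capture on the CRF therefore cannot be excluded. This also stands, although the protocol should then say so.

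Finally, six against zero is the smallest such split to reach p < 0.05 at this size (five against zero gives p = 0.06), so the illustration shows an extreme case. It is offered only to show that the test-arm count cannot be interpreted alone.

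**Conclusion.** The point holds in a narrow form. Serious injuries outside the listed endpoints are reported only if attributed to PleuraFlow, and tube malfunction or replacement is not an outcome in either arm, so these events cannot be compared between randomised arms. The main clinical consequences of tube harm can be.

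The primary endpoint, its analysis and the sample size are unaffected. The effect on what the trial can say about other complications cannot be put in numbers from the documents, since no rate of tube injury or failure outside the endpoints is given. The conclusion assumes that the Manual of Operation does not already ask for these events in both arms. This is a cheap improvement to completeness, not a flaw that threatens the trial.

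**What to change.** Add an outcome to 2.13.3, with the same CRF question for every patient in both arms, covering tube insertion to 30 days after the index surgery:

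- any serious injury by the 11.1 definition, regardless of attribution;
- as a secondary item, any suspected tube involvement, PleuraFlow or standard;
- any tube malfunction, or replacement for blockage or dislodgement.

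Tabulate these descriptively by randomised arm. Starting at insertion captures placement injuries, and running to day 30 captures late ones. Attribution should stay secondary because the operating surgeon knows the assignment (10.5) and test patients may carry both kinds of tube.

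Reconcile 11.2 with the sponsor's undertaking in 14.4, and correct the cross-reference in 13.9. If the Manual of Operation already collects these events, cite it in the protocol. Leave the 48-hour and MDR vigilance reporting for PleuraFlow unchanged.

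The cost is some extra data entry from records already used as source data to day 30 (section 12), plus one descriptive table. Comparisons of rare injuries will remain imprecise at 254 per arm.

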#### Table 3: Manufacturer's Reporting Requirements and Timelines

PleuraFlow ® System: A) is marketed in the US B) has Canadian License C) has CE marking	US MDR Action File MedWatch Report (form	EU-MDV Action File Vigilance SystemReport		Canadian MPR Action File Mandatory Problem Report	
	3500A) to FDA	Incident occurred in EEA	Incident occurred outside EEA	Incident occurred in Canada	Incident occurred outside Canada
and	Reporting Timeframe for 2, 5, 10, & 30 day reports, start the day after the first Company employee is notified. Report is to be sent within the time specified below.				
a malfunction were to occur that requires immediate remedial action to prevent an unreasonable risk of substantial harm to the public health (or as described in MEDDEV 2.12-1 for the EU, Serious Public Health Threat).	Yes Initial Report 5 working days	Yes Initial Report immediately but not more than 2 calendar days	Yes Initial Report immediately but not more than 2 calendar days*	Yes On or before recall actions initiated; immediately without any delay which cannot be justified for serious public health issues	Yes On or before recall actions are initiated for any corrective action; immediately without any delay which cannot be justified serious public health
The FDA has identified an event, and submitted a written request to file a report, for all subsequent events of the same nature that involve similar devices for a specified time period.	Yes 5 working days	N/A	N/A	N/A	N/A
FDA and CMDR Information reasonably suggests a death or serious injury /	Yes 30 days	NA	NA	Yes Preliminary	Yes Preliminary

Rev. 4, Febuary 2016

deterioration of health has occurred and was caused or contributed to by a device manufactured by our company.				Report immediately without any delay which cannot be justified and not more than 10 days	Report immediately without any delay which cannot be justified and not more than 10 days if corrective action is initiated
MDD Information reasonably suggests a death or unanticipated serious deterioration of health has occurred and was caused or contributed to by a device manufactured by our company.	NA	Yes Initial Report immediately but not more than 10 calendar days	No	NA	NA
A malfunction has occurred with the PleuraFlow ® System and would be likely to cause or contribute to a death or serious injury if the malfunction were to recur.	Yes 30 days	Yes Initial Report immediately but not more than 30 calendar days	No	Yes Preliminary Report immediately without any delay which cannot be justified and not more than 30 days	Yes Preliminary Report immediately without any delay which cannot be justified and not more than 30 days if corrective action is initiated
Additional information becomes available after the initial report has been submitted.	Supplemental Report	Final Report	NA	Final Report	Final Report
A systematic Recall has been initiated due to risk of Death or Serious Injury (reported to a Regulatory Agency)	Yes Submit Report Within 10 working days of initiating action	Yes On or before initiating recall actions	Yes On or before initiating recall actions	Yes Before and after initiating recall actions	Yes On or before recall action; indicating to or requested to take such actions by a Regulatory Agency

# 12 Data

Data is collected on Case Report Forms (CRFs). Electronic Data Capture (EDC) system will be used to enter data. Manual (paper) CRF samples are provided in the study Manual of Operation.

Source data shall be used to complete the study CRF. Source data consist of all information in the patient health record with the exception of Personal Health information (PHI). These include hospital records, records from doctor office visits, clinic visits, hospital re-admission after discharge and up to 30 days after the index surgery, laboratory results and clinical staff notes.

Source documents, if not in electronic format, should be completed legibly, in dark ink, typewritten or generated by testing equipment. Any necessary corrections should be made by a single strikethrough in ink, initialed and dated by the person who makes the change on the day the change is made.

Upon CRF completion, the Investigator should sign and date each CRF that bears a signature line. Completed CRFs shall be monitored and collected during periodic site visits. Source documents and copies of CRFs shall be available for review by the study sponsor, monitor and authorized regulatory bodies.

#### **12.1** Protection of Patient Privacy and Confidentiality of Patient Information

The PMCF study will be conducted in accordance with GCP. Subject confidentiality shall be maintained at all times throughout the conduct of this trial and all subject data shall be maintained secure against unauthorized access. Possible review and photocopying of the subject's records by the IRB, Health Canada or FDA representatives could occur. In addition, ClearFlow, Inc., the manufacturer, and its representatives will review and photocopy anonymized subjects' records as part of monitoring activities aimed at assuring the accuracy of the data collected from the subject health record per requirements of this study protocol.

All data entered into the database are anonymized. Patient Health Information (PHI) will not be collected.

Identifiable information of all subject records to be reviewed per the above must be blacked out (de-identified) and only the subject's study number used as tracking information. Individual subject's data will not be used for educational, presentation and/or publication purposes.

Photographs of the chest tubes used in this study may be taken after removal from the patient to document chest tube patency.

Regulatory agencies and ClearFlow, Inc. are required to maintain the privacy of all records they review in connection with this study.

The user interface to the EDC is password protected. Only approved site personnel, trained on the use of EDC will be allowed password-protected access to the EDC for the purpose of data entry. All study documents and data elements will identify patients by their unique subject identification (ID) number.

